6.1. Adverse Events

The verbatim terms used in the eCRF by investigators to identify AEs will be coded using the Medical Dictionary for Regulatory Activities (MedDRA). Treatment-emergent AEs (TEAEs) are AEs with onset during the intervention phase or that are a consequence of a pre-existing condition that has worsened since baseline. All reported AEs which are treatment-emergent will be included in the analysis. For each AE, the count and percentage of participants who experience at least 1 occurrence of the given event will be summarized by intervention group.

The following analyses of TEAEs will be used to assess the safety of participants:

- Frequency and type of AEs
- Frequency and type of SAEs
- Frequency and type of reasonably related AEs as assessed by the investigator
- Frequency and type of AEs leading to discontinuation of study intervention
- Frequency and type of infections (including COVID-19 infections)
- Frequency and type of serious infections
- Frequency and type of infections requiring oral or parenteral antimicrobial treatment
- Frequency and type of AEs temporally associated with infusion
- Frequency and type of injection-site reactions

Since safety should be assessed relative to exposure and follow-up, all AE summary tables will summarize the average weeks of follow-up and average exposure (number of administrations) for each treatment group.

In addition to the summary tables, a by-subject listing will be provided for deaths that occurred during the study and, respectively, for the following TEAEs:

1. SAEs
2. AEs that led to permanent discontinuation of study intervention
3. Serious infections including TB
4. COVID-19 infections
5. Anaphylactic reactions or serum sickness reactions
6. Malignancies

6.2. Clinical Laboratory Tests

Routine laboratory data for hematology and clinical chemistry will be collected at study visits from Week 0 through Week 38 according to SoA in the Protocol Section 1.3. The following laboratory assessments will be collected:

1. Hematology: hemoglobin, hematocrit, platelet count, total and differential white blood cell count (WBC) count.
2. Chemistry: total and direct bilirubin, alanine aminotransferase (ALT), aspartate aminotransferase (AST), alkaline phosphatase, albumin, total protein, calcium, phosphate, sodium, potassium, chloride, blood urea nitrogen (BUN), and creatinine.

The following summaries of clinical laboratory tests will be provided for participants in the Safety Analysis Set (Section 2.2.3):

1. Summary of laboratory parameters and change from baseline in laboratory parameters over time
2. Plots of laboratory parameters and changes from baseline in selected clinical laboratory parameters over time
3. Summary of maximum NCI-CTCAE toxicity grade for postbaseline laboratory values
4. Shift tables for maximum NCI-CTCAE toxicity grade for selected laboratory parameters (hematology: hemoglobin, platelets, total WBC, absolute lymphocytes, and absolute neutrophils; chemistry: ALT, AST, and alkaline phosphatase) from baseline to corresponding postbaseline laboratory values
5. Summary of maximum postbaseline measurement for ALT, AST, alkaline phosphatase and total bilirubin relative to ULN
6. Summary of maximum postbaseline elevated liver function tests (AST or ALT > 5xULN)
7. Patterns of change in ALT and AST will be assessed by summarizing the number of participants with only one ALT/AST > 1 ULN or ≥ 3 ULN or ≥ 5 ULN; with 2 or more consecutive ALT/AST measurements >1 ULN or ≥ 3 ULN or ≥ 5 ULN; with 2 or more non-consecutive ALT/AST measurements
8. Summary of laboratory data missed or collected outside window due to COVID-19 Pandemic

The baseline value for a participant is the value closest to but prior to the first dose of study agent. In addition, change from baseline is defined to be the assessment at the postbaseline visit minus the assessment at baseline. There will be no imputation for missing laboratory values.

Clinical laboratory test values are to be graded based on National Cancer Institute Common Terminology Criteria for Adverse Events (NCI-CTCAE) version 5.0 ([Attachment 7](#)). The laboratory tests not included in Attachment 7 will not be presented in the corresponding tables or listings.

Listings of participants with any abnormal post-baseline laboratory values of NCI-CTCAE grade ≥ 2 and maximum postbaseline elevated liver function tests (AST or ALT $> 5 \times \text{ULN}$) will also be provided.

6.3. Other Safety Parameters

6.3.1. Suicidal Ideation and Behavior

The Columbia-Suicide Severity Rating Scale (C-SSRS) will be used as a screening tool to prospectively evaluate suicidal ideation and behavior in this study, as part of a comprehensive evaluation of safety. The C-SSRS is an investigator-administered questionnaire that defines 5 subtypes of suicidal ideation and 4 possible suicidal behaviors, as well as self-injurious behavior with no suicidal intent and completed suicide, and is a fully-structured subject self-report questionnaire, including standardized questions, follow-up prompts, error handling routines, and scoring conventions^{8,9}.

The baseline is defined as the most severe/maximum score at screening and Week 0. Suicidal ideation and behavior will be summarized by the most severe/maximum post baseline outcome. A shift table from baseline to post-baseline will also be provided. Participants with positive (i.e., score > 0) ideation and behavior will be presented in a data listing.

7. PHARMACOKINETICS/PHARMACODYNAMICS

7.1. Pharmacokinetics

PK analyses will be based on the PK Analysis Set (Section 2.2.4). Participants will be analyzed according to the study intervention that they actually received, regardless of the treatments they are randomized to. No imputation for missing data will be performed.

7.1.1. Serum Guselkumab and Golimumab Concentrations

Blood samples for determining the serum guselkumab and golimumab concentrations will be drawn from all participants according to the Schedule of Activities in the Protocol. Unless otherwise mentioned, serum guselkumab and golimumab concentration summaries will be provided by study intervention at each visit through Week 12 and through Week 38. Descriptive statistics of the serum guselkumab and golimumab concentrations will be calculated by treatment group at each sampling time point when appropriate, including n, arithmetic mean, SD, coefficient of variation (%CV), median, interquartile range, range (minimum and maximum). PK data may be displayed graphically. The following analyses will be performed as appropriate:

- Summary of serum guselkumab and golimumab concentrations at each visit by study intervention

- Proportion of participants without detectable serum guselkumab and golimumab concentration (below the lower limit of quantification [$< \text{LLOQ}$]) at each visit by study intervention
- Summary of serum guselkumab and golimumab concentrations at each visit by study intervention and baseline body weight (quartiles)
- Plot of median serum guselkumab and golimumab concentrations over time by study intervention
- Plot of median serum guselkumab and golimumab concentrations over time by study intervention and baseline body weight (\leq median, $>$ median)

7.1.1.1. Data Handling Rules

Unless otherwise specified, the following data handling rules will apply to PK analyses:

- A concentration not quantifiable ($< \text{LLOQ}$) will be treated as 0 in the summary statistics and shown as ' $< \text{LLOQ}$ ' in the data listings.
- The data from a participant who meets 1 of the following dosing deviation criteria will be excluded from the by-visit data analyses from that point onwards:
 - Discontinued guselkumab or golimumab administrations.
 - Skipped a guselkumab or golimumab administration.
 - Received an incomplete/ incorrect dose.
 - Received an incorrect study agent.
 - Received an additional guselkumab or golimumab dose.

In addition, if a participant has an administration outside of dosing windows ([Table 4](#)), the sample data collected at that visit and after that visit prior to the next administration will be excluded from the by-visit data analyses.

Table 4: Dosing Window	
Visit	Window
Week 0 through Week 38	± 4 days from scheduled visit day
Final Safety and Efficacy Follow-up visits	± 7 days from scheduled visit day

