4. STUDY DESIGN

4.1. Overall Design

This is a Phase 2a, randomized, double-blind, active-controlled, parallel-group, multicenter, interventional POC clinical study designed to evaluate the efficacy and safety of combination therapy with guselkumab and golimumab in adults with moderately to severely active UC. The target population is men or women 18 to 65 years old with moderately to severely active UC, as defined by a Mayo score of 6 to 12, inclusive, at baseline, including an endoscopy subscore ≥ 2 as obtained during the central review of the video endoscopy. Participants must be naïve to TNF antagonists and have failed or not tolerated conventional therapy with oral or IV corticosteroids or immunomodulators (6-mercaptopurine [6-MP] or AZA).

This study will consist of 2 distinct phases: a 12-week combination comparison phase followed by a 26-week monotherapy phase. At Week 0, a target of 210 participants will be randomized in a 1:1:1 ratio to either combination therapy with guselkumab and golimumab, guselkumab monotherapy, or golimumab monotherapy, stratified by the concomitant use of corticosteroids at baseline (Y/N). Participants randomized to combination therapy will receive guselkumab monotherapy after Week 12. Participants randomized to a monotherapy group will continue on their originally randomized monotherapy after Week 12. The combination therapy arm will employ the same dose regimens of guselkumab and golimumab being used in the respective monotherapy intervention groups to facilitate scientific interpretation of the results. The following is a description of the 3 intervention groups:

- **Combination therapy:** guselkumab 200 mg IV and golimumab 200 mg SC at Week 0; golimumab 100 mg SC at Weeks 2, 6, and 10; guselkumab 200 mg IV at Weeks 4 and 8 followed by guselkumab 100 mg SC q8w
- **Guselkumab monotherapy:** guselkumab 200 mg IV at Weeks 0, 4, and 8 followed by guselkumab 100 mg SC q8w
- **Golimumab monotherapy:** golimumab 200 mg SC injection at Week 0, followed by golimumab 100 mg at Week 2 and then golimumab 100 mg every 4 weeks (q4w)

In addition, placebo administrations (IV or SC) will be given, as appropriate, to maintain the blind throughout the duration of the study. Refer to Study Intervention (Section 6) for additional details.

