6. STUDY INTERVENTION

6.1. Study Interventions Administered

- All participants will receive an IV infusion of either guselkumab or placebo at Weeks 0, 4, and 8.
- All participants will receive 1 SC injection of either guselkumab or placebo at Weeks 16, 24, and 32.
- All participants will receive 2 SC injections of either golimumab or placebo at Week 0, and 1 SC injection of either golimumab or placebo at Weeks 2, 6, 10, 14, 18, 22, 26, 30, and 34.

For the baseline (W0) visit, the IV study intervention should be administered first. The SC study intervention should be administered approximately 30 minutes after the IV study intervention infusion is complete. If multiple SC injections are administered within the administration visit, each injection of study intervention should be given at a different location of the body.

Study intervention administration must be captured in the source documents and the electronic case report form (eCRF).

Guselkumab and golimumab and the corresponding placebo for each intervention will be manufactured and provided under the responsibility of the sponsor. Refer to the respective IBs for a list of excipients. Detailed instructions on the administration of study intervention will be provided in the site Investigational Product Procedures Manual (IPPM) and Investigation Product Preparation Instructions (IPPI).

Guselkumab

Guselkumab will be supplied as a 100 mg/mL sterile liquid in a single dose prefilled syringe (PFS) assembled in an UltraSafe Plus™ Passive Needle Guard (PFS-U). Placebo for guselkumab will be supplied as a 1 mL sterile liquid in a single dose PFS assembled in a PFS-U. The single dose PFS-U will support both IV preparations and SC administrations.

Golimumab

Golimumab for SC injection will be supplied as a 100 mg/mL sterile liquid in a single-use PFS. Placebo for golimumab for SC injection will be supplied as a 1 mL sterile liquid in a single-use PFS.

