1.2. Trial Design

[figure not shown]
This is a Phase 2a, randomized, double-blind, active-controlled, parallel-group, multicenter, interventional proof-of-concept (POC) clinical study designed to evaluate the efficacy and safety of combination therapy with guselkumab and golimumab in adults with moderately to severely active UC. The target population is men or women 18 to 65 years old with moderately to severely active UC, as defined by a Mayo score of 6 to 12, inclusive, at baseline, including an endoscopy subscore ≥ 2 as obtained during the central review of the video endoscopy. Participants must be naïve to tumor necrosis factor (TNF) antagonists and have failed or not tolerated conventional therapy with oral or intravenous (IV) corticosteroids or immunomodulators (6-mercaptopurine [6-MP] or azathioprine [AZA]).

This study will consist of 2 distinct phases: a 12-week **combination comparison phase** followed by a 26-week **monotherapy phase**. At Week 0, a target of 210 participants will be randomized in a 1:1:1 ratio to either combination therapy with guselkumab and golimumab, guselkumab monotherapy, or golimumab monotherapy, stratified by corticosteroid use at baseline (yes, no). Participants randomized to combination therapy will receive guselkumab monotherapy after Week 12. Participants randomized to a monotherapy group will continue on their originally randomized monotherapy after Week 12. The combination therapy arm will employ the same dose regimens of guselkumab and golimumab being used in the respective monotherapy intervention groups to facilitate scientific interpretation of the results. The following is a description of the 3 intervention groups:

- **Combination therapy (N = 70):** guselkumab 200 mg IV and golimumab 200 mg subcutaneous (SC) at Week 0; golimumab 100 mg SC at Weeks 2, 6, and 10; guselkumab 200 mg IV at Weeks 4 and 8 followed by guselkumab 100 mg SC q8w
- **Guselkumab monotherapy (N = 70):** guselkumab 200 mg IV at Weeks 0, 4, and 8 followed by guselkumab 100 mg SC q8w
- **Golimumab monotherapy (N = 70):** golimumab 200 mg SC injection at Week 0, followed by golimumab 100 mg at Week 2 and then golimumab 100 mg every 4 weeks (q4w)

In addition, placebo administrations (IV or SC) will be given, as appropriate, to maintain blinding throughout the duration of the study. Refer to Protocol Section 6 for additional details. A diagram of the study design is provided in [Figure 1](#).

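### SAP 7.1.1.1 sets PK exclusions per participant and sample, not per measured drug, so in the alternating schedule valid concentrations are dropped and mistimed troughs can be kept

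*SAP*

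**What the plan says.** SAP 7.1.1.1 contains two exclusion rules.

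- **Permanent rule.** A participant who meets one of five dosing-deviation criteria is "excluded from the by-visit data analyses from that point onwards". Three of the five name the drugs jointly, for example "Skipped a guselkumab or golimumab administration" and "Discontinued guselkumab or golimumab administrations". The other two (incomplete or incorrect dose, incorrect agent) name no drug.
- **Window rule.** If a dose falls outside plus or minus "4 days from scheduled visit day", "the sample data collected at that visit and after that visit prior to the next administration will be excluded from the by-visit data analyses".

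Neither rule names the analyte. The window rule does not say whose next dose ends the exclusion, or whether a placebo dose counts.

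The combination schedule in SAP 1.2 starts both drugs at Week 0, then gives "golimumab 100 mg SC at Weeks 2, 6, and 10; guselkumab 200 mg IV at Weeks 4 and 8". Dosing visits are the same in all arms, with placebo filling the gaps. Protocol 6.1 states, for example, "All participants will receive an IV infusion of either guselkumab or placebo at Weeks 0, 4, and 8". Under Protocol 8.5.1 every PK sample is split into separate aliquots for guselkumab and golimumab. Protocol 9.4.3 leaves the detailed PK exclusion rules to the SAP, and no other section makes them drug-specific.

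**The concern.** These rules would suit a one-drug trial. Here two drugs are given on different days and measured in the same tube, so a deviation in one says nothing about whether the other was dosed correctly.

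Two errors follow. Sound concentrations of the correctly dosed drug can be discarded. Concentrations of the mistimed drug can re-enter the summary before that drug is next given.

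PK of the combination is a secondary objective (Protocol 3.1.2, SAP 1.1). SAP 7.1.1 summarises both drugs by treatment group and visit. A reader comparing a drug's level alone with its level in combination will use those tables, so the exclusions should not depend on the other drug's dosing record.

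**Working it through.** **Inputs.** Dose weeks come from SAP 1.2 and Protocol 6.1. PK samples are at Weeks 0, 2, 4, 6, 8, 10 and 12, pre-dose at dosing visits (Protocol 1.3, Table 1 and its footnote on PK sampling). The window is ±4 days, with visits anchored to the randomization date.

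**Dose count.** Guselkumab at Weeks 0, 4, 8 gives 3; golimumab at Weeks 0, 2, 6, 10 gives 4. This matches the 3 and 4 overlapping doses stated in Protocol 2.3.

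**Permanent rule.** A combination participant skips Week 2 golimumab but receives every guselkumab dose correctly. Guselkumab values at Weeks 4, 6, 8, 10 and 12 are excluded: 5 sound values by Week 12, and later ones too. A guselkumab-arm participant has no golimumab dose to skip, so this loss cannot arise there under the criteria that name the drugs.

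**Window rule, combination arm, one late dose at a time.** Samples drawn at the late visit itself are not counted, because they are off nominal time for both drugs.

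| Late dose | Exclusion ends at | Sound value dropped | Affected value kept |
|---|---|---|---|
| W2 golimumab | W4 guselkumab | W4 guselkumab | W6 golimumab |
| W4 guselkumab | W6 golimumab | W6 golimumab | W8 guselkumab |
| W6 golimumab | W8 guselkumab | W8 guselkumab | W10 golimumab |
| W8 guselkumab | W10 golimumab | W10 golimumab | W12 guselkumab |
| W10 golimumab | after W12 | W12 guselkumab | none by W12 |

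The total is 5 sound values dropped and 4 affected values kept.

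**Three readings of the administration that ends the exclusion, through Week 12 (dropped / kept).**

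- *Active doses only:* combination 5 / 4; each monotherapy arm 0 / 0. A late Week 8 infusion leaves the Week 12 guselkumab value in for the combination arm (next active dose Week 10) and removes it in the guselkumab arm (next active dose Week 16).
- *Placebo counts:* combination still 5 / 4, but each drug is handled alike across arms: guselkumab 3 / 2 in the combination and guselkumab arms, golimumab 2 / 2 in the combination and golimumab arms.
- *Next dose of the same drug, whole sample excluded:* combination 9 / 0; each monotherapy arm 0 / 0.

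**Size of a retained error.** Take the Week 8 infusion L days late and the Week 12 sample on time. Assume equal doses, simple superposition and a half-life h of 14 to 18 days; the half-life is not in the documents. The ratio to the on-time trough is

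[2^(−84/h) + 2^(−56/h) + 2^(−(28−L)/h)] / [2^(−84/h) + 2^(−56/h) + 2^(−28/h)].

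L = 5 is the first day outside the window. L = 9 is the last day before the Week 10 window opens (day 70 − 4 = 66, which is day 56 + 10).

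- h = 18, L = 5: (0.0394 + 0.1157 + 0.4124) / (0.0394 + 0.1157 + 0.3402) = 0.5675 / 0.4953 = 1.15.
- h = 14, L = 9: (0.0156 + 0.0625 + 0.3904) / (0.0156 + 0.0625 + 0.2500) = 0.4685 / 0.3281 = 1.43.

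**After the fix below.** The combination arm goes from 5 / 4 on the active-dose reading to 0 / 0, and the same late dose is treated identically in every arm.

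**The case against.** **Arm inequality under the window rule.** A reader might infer that this rule necessarily treats the arms unequally. The documents do not support that. SAP 2.2.4 glosses study intervention as golimumab or guselkumab, but SAP 1.2 and Protocol 4.1 also speak of placebo administrations. If placebo counts, each drug is handled alike across arms. What survives is that both misclassifications then occur in every arm.

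**Golimumab discontinued by design.** A reader might infer that every combination participant meets the discontinuation criterion after Week 10, since "Participants randomized to combination therapy will receive guselkumab monotherapy after Week 12". That is strained. The criterion is listed as a dosing deviation, the end of golimumab is the planned regimen, and SAP 7.1.1 plans summaries of both drugs through Week 38. It merits one clarifying sentence, no more.

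**Unequal loss as a percentage.** With 7, 3 and 4 active doses, an assumed independent 2% deviation rate per dose gives 1 − 0.98^7 = 13.2%, 1 − 0.98^3 = 5.9% and 1 − 0.98^4 = 7.8% with at least one trigger. The rate is invented, and the 7 doses fall on 6 visits. Discontinuation is also defined for study intervention as a whole (Protocol 7.1), so it does not scale with the dose count. These figures illustrate direction only.

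**A larger trough error.** The single-dose formula 2^(10/h) for a 10-day delay gives 1.47 to 1.64. It ignores carry-over from Weeks 0 and 4; with carry-over the range is 1.32 to 1.49. A 10-day delay also reaches the Week 10 window and might be recorded as a skipped dose, which would remove the value.

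**Dropping both drugs is deliberate.** Guselkumab levels in someone who missed golimumab no longer reflect full combination dosing, so excluding both could be a conservative choice. That is arguable for the permanent rule, but the SAP does not give it as the reason. It cannot explain keeping a mistimed trough.

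**Limited consequence.** This stands. By-visit PK is descriptive with no formal between-arm test, and the PK-efficacy quartiles in SAP 7.1.2 are optional.

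**Conclusion.** The point holds as a defect in a stated rule. On all three readings of the window rule, sound concentrations of the other drug are discarded in the combination arm. On two of the three, mistimed troughs are kept; on the third none are kept, but more sound values are lost (9 against 5). The permanent rule's loss of the correctly dosed drug falls on the combination arm wherever the criteria name the two drugs. For the two criteria that do not, whether placebo counts is again open.

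A retained Week 12 guselkumab trough would be about 1.15 to 1.4 times its on-time value for a 5- to 9-day delay, given the assumed half-life and superposition. The number of participants affected cannot be derived from the documents. Efficacy analyses are untouched, and population PK (SAP 7.1.3) has its own document. Because different programmers could build different datasets from the same text, the wording should be settled before the by-visit PK tables are produced.

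**What to change.** Apply SAP 7.1.1.1 separately to each measured drug:

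- A dosing deviation in one drug excludes only that drug's concentrations.
- After an out-of-window dose of a drug, exclude that drug's samples up to and including the pre-dose sample at its next active dose.
- As a clarification only, state that the planned end of golimumab after Week 10 in the combination arm is not a discontinuation for these rules.

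The cost is revised wording and one set of exclusion flags per drug instead of one per participant. No new samples or assays are needed.
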